## Contraceptives

Female subjects of childbearing potential (excluding postmenopausal women, sterilized, ovariectomized, and hysterectomized women) must agree to use 2 generally accepted adequate contraceptive methods of which 1 is a barrier method (e.g., hormonal contraception stabilized for at least 1 month [oral, patch, depot, injectable, vaginal ring] in combination with condom by partner) or should agree upon continuous abstinence from heterosexual contact from screening until at least 6 months after last dosing.

No additional contraceptive method is needed in case of surgical sterilization (at least 3 months prior to screening), hysterectomy, or a partner who has been vasectomized (at least 3 months prior to screening).

Male subjects should use condoms for the duration of the study and for at least 6 months after last administration of study drug.

## Other

During the study, no alcohol abuse or drug abuse is allowed.

## 3.3.7. TREATMENT COMPLIANCE

To ensure treatment compliance, medication dosing will be supervised by the Investigator or his/her designee at all visits.

The exact times of study drug dosing at the clinical site will be recorded in the (e)CRF. Compliance will be further confirmed by bioanalytical assessment of ALX-0061 in serum samples. Treatments that are administered outside of the scheduled windows, as well as missed visits, will be recorded on the (e)CRF.

---

All subjects' (e)CRFs will be monitored by a site monitor (also see section [5.2.4](#)).

### **3.3.8. RANDOMIZATION**

After obtaining oral and written informed consent, subjects will be screened according to the inclusion and exclusion criteria and will receive a unique subject identification (ID) number, assigned by IWRS. The site will contact IWRS, provide details of the site and the subject, and receive a subject ID number for the subject.

At randomization, subjects will be reassessed and, if they meet the specified entry criteria, subjects will be randomly assigned to 1 of 5 treatment groups in a 1:1:1:1:1 ratio, and will receive a randomization number just prior to dosing according to the randomization scheme.

## **3.4. ASSESSMENTS**

### **3.4.1. TIMING OF ASSESSMENTS**

Written informed consent will be obtained before the first study-related procedure.

After informed consent has been obtained, each subject will be assigned a unique subject ID number.

AEs and previous/concomitant medications will be recorded from the study inclusion date (ICF signed) to the subject's last visit.

#### **3.4.1.1. ELIGIBILITY PROCEDURES**

At screening, which will take place within 21 to 1 day before the first administration of study drug, subjects will be asked to attend the clinical site to be screened according to the inclusion and exclusion criteria (section 3.2) and to have other assessments performed as specified in the [Schedule of Assessments](#).

Subjects who signed an informed consent form, but do not meet the eligibility criteria and are not randomized, will be designated a screen failure. Subjects who meet all eligibility criteria but discontinue from the study for other reasons (eg, subject request) will not be considered screen failures.

Data of all subjects screened will be collected in the (e)CRF in order to assess the numbers and characteristics of the excluded subjects, and the reasons for their exclusion.

The results from the screening procedures needed to evaluate eligibility must be available prior to the first administration of the study drug. Sites will use the central laboratory selected for the study to analyze screening samples and to use these reported values to determine eligibility.

Unscheduled visits may be planned to assess, confirm, and follow up on clinically relevant AEs or laboratory abnormalities. Findings made during these unscheduled visits should be reported in the designated sections of the (e)CRF.

### **3.4.1.2. TREATMENT AND ASSESSMENT PERIOD**

#### **Week 0 (Baseline)**

For details with regard to randomization, please refer to section [3.3.8](#).

On Week 0/Day 0, assessments and procedures should be performed as outlined in the [Schedule of Assessments](#).

#### **Post-Randomization Assessments**

Eligible subjects will receive treatment from Week 0 up to and including Week 22. Subjects will return for 13 ambulatory visits planned at Weeks 0, 2, 4, 6, 8, 10, 12, 14, 16, 18, 20, 22, and Week 24.

An End of Treatment Visit will be performed at Week 24.

For subjects who discontinue due to fulfilling the **efficacy** discontinuation criteria (see section [3.2.3.2](#)) at weeks 12, 16, or 20, the visit at which they meet these discontinuation criteria is defined as the Early Termination Visit.

Subjects who discontinue early for reasons other than the efficacy discontinuation criteria should have an Early Termination Visit 2 weeks after the last study drug administration (unless they discontinue during a study visit in which case that visit becomes their Early Termination Visit).

All assessments will be performed at the visits as indicated in the [Schedule of Assessments](#).

All post-baseline visits may occur at the indicated week  $\pm$  3 days throughout the study versus the date of the Baseline Visit.

At Week 12, 16, or 20, any subject with < 20% improvement in both SJC and TJC (66/68 counts) will have to discontinue from the trial but remain blinded to study drug assignment. The IWRS will be used to qualify subjects for study drug discontinuation based on non-response defined as < 20% improvement in both SJC and TJC.

**Missed visits:**

- If a subject misses a visit but a new visit can be performed within 1 week of the originally planned missed visit (i.e., within 3 weeks of the previous visit), then all assessments per missed visit should be performed at this new visit and the study staff should administer the study drug to the subject and maintain the subject's original injection schedule. In case of rescheduling of missed visits, total duration of the assessment period should remain 24 weeks.
  - For example, if a subject receives the first dose of study drug on January 1st, that is considered "Day 0 (Week 0) of the study"; the next target day of administration will be January 15th.
  - If the subject misses this second visit and comes in on January 19th (i.e. within 3 weeks of the previous visit), then the study staff should administer the study drug on that day. The next visit should be scheduled for January 29th (i.e. 4 weeks after January 1st).
- If a subject misses a visit and the visit can only be performed later than 3 weeks of the previous visit, the site should contact the CRO.
- If a subject misses a dose of MTX on their regularly scheduled dosing date, they should take the forgotten dose as soon as they remember; however, if more than 72 hours have elapsed since the missed dose, the subject should contact the Investigator for further dosing instructions.

For all subjects, injections should not occur less than 1 week apart. The CRO/Sponsor should be contacted if this cannot be respected. In case of interruption of 2 consecutive drug administrations, the subject should be discontinued from the study.

### **3.4.1.3. END OF TREATMENT VISIT AND FOLLOW-UP**

Subjects who are eligible to participate in the OLE study, will have the End of Treatment Visit at Week 24, and no further Follow-up Visit.

Subjects who are not eligible to participate in the OLE study and who received all study drug up to and including Week 22, should return for the Week 24 End of Treatment Visit, and for the Follow-up Visit approximately 12 weeks after the last study drug administration.

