#### **Study Duration:**

- The anticipated study duration is a maximum of 34 weeks after randomization:
  - Subjects who will not participate in the OLE study will be followed for efficacy up to and including Week 24, and for safety up to and including Week 34.
  - Subjects who will participate in the OLE study will be followed until Week 24, at which time they will switch to the OLE.

The end of study is defined as the time of the last visit of the last subject participating in the study.

- Screening period:
  - Subjects will be screened to confirm eligibility for participation in this study within 3 weeks prior to first dosing.
- Treatment and assessment period:
  - All eligible subjects will receive treatment from Week 0, up to and including Week 22. Subjects will return for 13 ambulatory visits planned on Weeks 0, 2, 4, 6, 8, 10, 12, 14, 16, 18, 20, 22, and 24.
- End of Treatment Visit (Week 24) (or Early Termination Visit for subjects who discontinue early)/Follow-up Visit:
  - Subjects who are eligible to participate in the OLE study will have the End of Treatment Visit in Study ALX0061-C201 at Week 24.
  - Subjects who are not eligible to participate in the OLE study will have the End of Treatment Visit at Week 24 and should return for a Follow-up Visit 12 weeks after last study drug administration.

---

- For subjects who will discontinue study participation for fulfilling the **efficacy** discontinuation criteria (see section 3.2.3.2) at weeks 12, 16, or 20, the visit at which subjects will meet these discontinuation criteria is defined as the Early Termination Visit. These subjects should return for a Follow-up Visit 12 weeks after last study drug administration.
- Subjects who have to discontinue early for reasons other than the efficacy discontinuation criteria, but are not withdrawing consent for post-treatment follow-up, should return for an Early Termination Visit 2 weeks after the last study drug administration (unless they discontinue during a study visit, in which case that becomes their Early Termination Visit). Subjects should also return for a Follow-up Visit 12 weeks after last study drug administration.
- Subjects who terminate study participation for reasons of lost to follow-up, informed consent withdrawal, or death will not have any follow-up assessments.

---

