Short Form (36) Health Survey (SF-36)		X						X		X		X		X		X	X
Functional Assessment of Chronic Illness Therapy – Fatigue (FACIT-Fatigue)			X						X		X		X		X	X	
Physician and patient global assessment Disease Activity			X	X	X	X	X	X	X		X		X		X	X	
Rheumatoid factor	X																
Anti-cyclic citrullinated peptide (CCP) antibodies	X																
Adverse events (AEs) L																→	
Pharmacokinetic (PK) samples M		X	X	X	X	X	X	X		X		X		X		X	X
Pharmacodynamic (PD) biomarker (total sIL-6R) M		X	X	X	X		X	X		X		X		X		X	X
Joint biomarkers (MMP-3, CXCL13) M	X	X	X	X				X						X			
Immunogenicity samples M	X	X		X		X				X				X		X	X

A. All assessments are to be completed prior to study drug administration, except for subjects who discontinue study drug injections. The order of assessments if more than 1 assessment is planned at the same time should be performed according to the following principles: vital signs should be assessed prior to blood sampling; patient reported outcomes should occur prior to the physician's joint evaluation and study drug should be dosed after all other assessments have been performed.

B. All post baseline visits may occur at the indicated week  $\pm$  3 days throughout the trial.

C. The Early Termination Visit is to be performed 2 weeks after the last study drug dosing for subjects who discontinue from the trial for other reasons than described in the efficacy discontinuation criteria (see section 3.2.3.2), unless they discontinue during a study visit, in which that becomes their Early termination Visit. For subjects who will meet the efficacy discontinuation criteria at Week 12, 16, or 20, the visit at which subjects will meet these discontinuation criteria is defined as the Early Termination Visit.

D. To be performed for each subject, except in case the subject enrolls in the open-label extension study (OLE).

- E. Vital signs (assessment after 5 min in supine position) will include height, weight, blood pressure, pulse, and temperature. A height measurement is only required at the Screening Visit. In case (PK) blood sampling is to be performed at the same visit, the vital signs assessment is to be performed prior to the blood sampling.

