**Figure 1: Overview of the design of Study ALX0061-C201**

MTX: methotrexate; OLE: open-label extension study ALX0061-C203 (in countries where study ALX0061-C203 is approved, eligible subjects who complete the 24-week assessment period of the current study will be invited to roll-over). q2w: every 2 weeks, q4w: every 4 weeks.

Subjects will be randomly assigned to receive ALX-0061 and/or placebo s.c. injections at Week 0 and every 2 weeks (q2w) thereafter, on top of their stable dose of MTX, up to and including Week 22.

The dosing regimens have been determined based on:

- Expected DAS28 response, ensuring characterization of the exposure-response curve (PK/PD modelling approach).
- Safety margins calculated by using the relevant observed exposure in nonclinical studies (cynomolgus monkey) versus the model-predicted human exposure of the selected dosing regimens for the clinical studies.
- Operational feasibility aspects for the study.

A PK-PD model, developed based on data pooled from Studies ALX-0061-1.1/10 and ALX0061-C102, was used to predict the response (in terms of DAS28) at different dose levels/regimens. The s.c. dose regimens 75 mg q4w, 150 mg q4w, 150 mg q2w and 225 mg q2w were selected as these are expected to be spread over the different levels of effect (low, medium, high), based on exposure-response modelling (PK-DAS28) of ALX-0061. Moreover, these regimens are covered by adequate safety margins when comparing the model predicted human exposure with the observed exposure in the toxicity studies.

In view of the availability of effective RA therapies and the current focus on early control of disease activity, prolonged treatment with placebo or ineffective therapies is considered unethical. Therefore, the proposed study includes provisions for study drug discontinuation for non-responding subjects at Week 12, 16, or 20. Subjects with < 20% improvement over baseline in both swollen joint count (SJC) and tender joint count (TJC) (66/68 counts) will discontinue from the trial but remain blinded to study drug assignment. Any future care will then be provided (outside of the study) at the discretion of the physician as part of usual clinical practice.

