##### **Efficacy discontinuation criteria at a Week 12, 16 or 20:**

Any subject with < 20% improvement from baseline in both swollen and tender joint count (SJC and TJC; 66/68 counts) at any of the visits at week 12, 16 or 20 will discontinue from the trial, but remain blinded to study drug assignment. The visit at which subjects will meet the efficacy discontinuation criteria, is defined as the Early Termination Visit for these patients. Subjects who have to discontinue study drug but are not withdrawing consent for post-treatment follow-up, should return for the Follow-up Visit, planned 12 weeks after the last study drug administration, according to section 3.4.1.3.

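### Section 3.4.1.3 drops the 12-week Follow-up Visit for subjects eligible for the open-label extension, while the Schedule of Assessments drops it only for those who enroll

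*Combined protocol and SAP*

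**What the plan says.** Four places in the protocol decide which Week 24 completers return for the Follow-up Visit.

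- **Section 3.4.1.3, first sentence.** Subjects who are "eligible to participate in the OLE study, will have the End of Treatment Visit at Week 24, and no further Follow-up Visit". The criterion is eligibility, and the exclusion is explicit.
- **Section 3.4.1.3, second sentence.** The visit goes to subjects who are not eligible "and who received all study drug up to and including Week 22, should return for the Week 24 End of Treatment Visit", and then for the Follow-up Visit. A condition on doses received is added to ineligibility.
- **Synopsis, Study Duration.** The opening bullets split by participation: "Subjects who will participate in the OLE study will be followed until Week 24, at which time they will switch to the OLE", whereas "Subjects who will not participate in the OLE study will be followed for efficacy up to and including Week 24, and for safety" to Week 34. The End of Treatment bullets lower in the same section split by eligibility: "Subjects who are not eligible to participate in the OLE study will have the End of Treatment Visit at Week 24" and come back 12 weeks after the last dose. The bullet for eligible subjects only places their Week 24 visit.
- **Schedule of Assessments, footnote D**, on the Follow-up Visit: "To be performed for each subject, except in case the subject enrolls in the open-label extension study (OLE"). The criterion is enrollment.

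The note to Figure 1 says that, where the OLE study is approved, "eligible subjects who complete the 24-week assessment period of the current study will be invited to roll-over".

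**The concern.** Eligibility and enrollment are different events. If eligible subjects are invited, some can decline, and for a decliner section 3.4.1.3 and footnote D give opposite instructions. No text says which one prevails.

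What is at stake is late safety information. Safety is part of the primary objective. Footnote L of the Schedule records adverse events through the Follow-up Visit, and section 3.5.1 ends the recording of treatment-emergent events at the subject's last visit. Section 3.1.1 plans anti-drug antibody measurement up to the Follow-up Visit, and the Schedule places laboratory and PK samples there. Under section 3.6.2 the safety, PD and immunogenicity analyses are run or repeated at the final database lock, after those visits. A subject released at Week 24 contributes none of this later information and, having declined the OLE, is not observed there either.

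**Working it through.** **Timing.** Inputs: last scheduled dosing at Week 22 (section 3.1.1), Follow-up Visit 12 weeks after the last dose (sections 3.1.1 and 3.4.1.3), End of Treatment Visit at Week 24, and up to 3 weeks of screening (section 3.1.1).

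- Follow-up Visit: 22 + 12 = Week 34. With screening, 3 + 34 = 37 weeks. Both match the protocol's own figures.
- Follow-up lost if the subject leaves at Week 24: 34 − 24 = 10 weeks.
- As a share of the period after the last dose: 10/12 = 83%. As a share of the time since randomization: 10/34 = 29%.

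The 12 weeks are counted from the last scheduled injection, active or placebo.

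**Who gets the visit.** Each type of Week 24 completer under each text:

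| Completer | Section 3.4.1.3 | Synopsis End of Treatment bullets | Synopsis duration bullets | Footnote D |
|---|---|---|---|---|
| (a) Enrolls in the OLE | No visit | Week 24 visit only | Followed to Week 24 | No visit |
| (b) Eligible, declines | **No visit** | Week 24 visit; Follow-up Visit not mentioned | **Safety to Week 34** | **Visit** |
| (c) Not eligible, all doses received | Visit | Visit | Safety to Week 34 | Visit |
| (d) Not eligible, one dose missed | Silent | Visit | Safety to Week 34 | Visit |

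Rows (a) and (c) agree throughout. Row (b) is a direct contradiction between section 3.4.1.3 on one side and footnote D and the duration bullets on the other. The End of Treatment bullets lean toward section 3.4.1.3 only by contrast: they give the visit to ineligible subjects and say nothing either way for eligible ones.

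Row (d) is an omission. There are 12 dosing visits (Weeks 0, 2, …, 22), and sections 3.2.3.2 and 3.4.1.2 require discontinuation only after 2 consecutive missed doses, so a subject can miss one and still complete Week 24. If the Week 22 dose is the one missed, the Follow-up Visit falls at 20 + 12 = Week 32, which is 8 weeks after Week 24. If a single earlier dose is missed, it stays at Week 34. The rest of section 3.4.1.3 concerns subjects who discontinue and does not clearly reach this completer. An eligible decliner who missed a dose belongs in row (b), not row (d).

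**The case against.** The best reply is that this is a slip in terminology and that the intended rule is plain. Footnote D is unambiguous, the duration bullets agree with it, and section 3.1.1 gives the Follow-up Visit as the general rule. Section 3.4.8 refers to the Schedule for the timing of all assessments, and a site working from the Schedule would lose nothing. All of that stands. It shows which text to keep, but it does not remove an explicit instruction to the contrary from the section devoted to this visit.

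A second reply is that an eligible decliner may not exist by definition. OLE eligibility is set in ALX0061-C203, which is not available. In the present protocol, willingness to consent and to follow the schedule are themselves entry criteria (inclusion criteria 10 and 11), and C203 may do the same. The synopsis and the body of section 3.1.1 invite subjects who complete Week 24 without naming eligibility, so only the Figure 1 note puts eligibility before the invitation. This stands as a real condition on the finding.

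Several stronger readings are tempting, and the documents do not support them:

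- A reader might infer that section 3.4.1.3 takes precedence because section 3.2.3.2 says subjects "should return for the Follow-up Visit, planned 12 weeks after the last study drug administration, according to section 3.4.1.3". That cross-reference concerns subjects who discontinue early, not Week 24 completers.
- A reader might infer that the synopsis also denies the visit to eligible subjects. It does not; only section 3.4.1.3 states the exclusion.
- A reader might infer that anyone who missed a dose and does not enter the OLE is left without follow-up. The silence reaches only the OLE-ineligible completer, whom footnote D and the matching synopsis bullet already cover. The all-doses phrase may simply have been meant to separate completers from discontinuers.
- A reader might infer that all safety oversight stops at Week 24. The Week 24 assessments are done, events that arose in the study are followed to a satisfactory outcome (section 3.5.5), related serious events are reportable at any time (section 3.5.2), and pregnancies for 6 months after the last dose (section 3.5.6.1).

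**Conclusion.** The inconsistency is real and should be corrected, but its reach is narrow. For an OLE-eligible subject who declines, section 3.4.1.3 withholds a visit that footnote D and the synopsis duration bullets require. At a site that follows section 3.4.1.3, each such subject would lose 10 of the 12 weeks of routine follow-up after the last dose, with the closing laboratory, PK and anti-drug antibody samples.

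This rests on two assumptions: that C203 does not treat unwillingness as ineligibility, and that some site reads section 3.4.1.3 literally. If either fails, nothing is lost through this conflict. The number of subjects affected cannot be derived from the documents and may be zero, so they give no basis for claiming a bias in the safety or immunogenicity comparison. The Week 12 ACR20 analysis and the power do not depend on this visit.

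The missed-dose gap is minor. It does not depend on how C203 treats unwillingness, but it is a silence in one section that other texts fill.

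**What to change.** Use enrollment as the single criterion in section 3.4.1.3 and in the two matching End of Treatment bullets of the synopsis. Suggested wording:

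> A subject who enrolls in the OLE study completes the present study at the Week 24 visit and has no Follow-up Visit. A subject who completes Week 24 and does not enroll, including an eligible subject who declines, returns for the Follow-up Visit 12 weeks after his or her last dose of study drug.

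Delete from section 3.4.1.3 the condition that all study drug through Week 22 was received. This closes both gaps however C203 defines eligibility.

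Footnote D and the synopsis duration bullets stay as they are. The general statements in section 3.1.1 on the Follow-up Visit and on the 37-week stay need no edit. Adding only an OLE exception to the latter would suggest that every other subject stays about 37 weeks, which is untrue of early discontinuers. For example, a subject who meets the efficacy criteria at Week 12 after a last dose at Week 10 is due for follow-up at 10 + 12 = Week 22.

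The cost is a wording change in two places, plus, for any non-enrolling completer who would otherwise have been released, one visit that the Schedule already contains.
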